4.2.1. Randomization

Subjects that meet the BM and Diary Compliance Criteria will be randomized using an automated interactive web response system (IWRS). The randomization schedule will be implemented in the automated interactive web response (IWR) system prior to kit distribution to the site. At the time of randomization the IWRS will assign a drug kit number for site personnel to dispense to the subject. Subjects will be stratified into one of the following two groups:

Group 1: Subjects < 65 years of age at time of randomization Group 2: Subjects ≥ 65 years of age at time of randomization

The site personnel must only dispense a drug kit that has been assigned by the IWRS. Dispensing kits out of order is considered a protocol violation.

Vital signs will be taken. Subjects will be queried for any adverse events or changes to their concomitant medications.

4.2.2. Study Drug

During Visit 2, subjects will be provided with instructions on how to take the study medication and rescue medication. One bottle of study drug (a 30 day supply) will be dispensed per subject along with one box of rescue bisacodyl. The study drug bottle will be weighed for drug accountability purposes. Subjects will take a daily dose of 2 capfuls of study powder until they return for Visit 3. Subjects will be instructed to return all medication (including bisacodyl) and components at Visit 3.

4.3. Treatment Period

4.3.1. Electronic Subject Diary during Treatment Period

Each day during the Treatment Period, subjects will complete their e-diary reporting. Subjects will report each bowel movement as it occurs along with related symptoms and characteristics (consistency, straining, urgency, completeness). Subjects will also report their daily study medication and rescue medication doses (if applicable) as they occur.

4.3.2. Treatment Day 1

Starting the morning of Treatment Day 1 (the day after randomization), subjects will measure two (2) capfuls of study medication and ingest it mixed in a beverage of their choice. When possible, subjects should take each dose at appromiately the same time every day (preferably in the morning). Subjects that develop persistent diarrhea or loose stools should contact their study center. Subjects with persistent diarrhea or loose stools will be allowed to adjust their dose down to 10.5g (1 capful) per day.

4.3.3. Visits 3 – 7 (Days 28, 56, 84, 112 and 140)

Subjects will return to the clinic every 4 weeks (+/- 2 days) for Visits 3 - 7. Vital signs (see section 4.1 for details) will be taken. Study personnel will weigh returned study medication bottles and count rescue bisacodyl tablets for accountability purposes and for consistency with the electronic diary reporting. Study personnel must discuss any electronic diary reporting irregularities (e.g. missed study medication or excessive rescue bisacodyl use, reporting compliance). Subjects will be queried for any adverse events or changes to their concomitant medications. Samples for chemistry, hematology, PK and urinalysis will be repeated as outlined in Section 4.1 (Note: serum pregnancy testing will be conducted at Visits 1, 5 and 8 only).

Subjects suspected by the Investigator of having developed lactic acidosis, characterized by abnormally low bicarbonate with abnormally high anion gap (deemed clinically significant by the investigator), should return for a redraw to test for lactate. Subjects with high lactate levels believed to be caused by the study medication should be discontinued.

A 30 day supply of study medication (1 bottle) along with 1 box of rescue bisacodyl will be dispensed at each visit. Unused product will not be redispensed. No rescue medication will be redispensed. Subjects will be instructed to bring all medication (including bisacodyl) and components at each follow up visit. Subjects that develop persistent diarrhea or loose stools should contact their study center. Subjects with persistent diarrhea or loose stools will be allowed to adjust their dose down to 10.5g (1 capful) per day.

At Visit 7 (Day 140), 2 bottles of study medication will be dispensed so that subjects have a sufficient supply to reach Visit 8 (Day 180).

4.3.4. Visit 8 – Day 180 (or Early Term)

Subjects will return at after a approximately 180 days of dosing (+4 days) for their final clinic visit. Vital signs will be taken. A 12-lead ECG will be performed by qualified, trained site personnel. ECG output must be reviewed by a physician investigator. A physical examination will be performed. Study personnel will weigh study medication bottles and count rescue bisacodyl tablets for accountability purposes and for consistency with the electronic diary reporting. Study personnel must discuss any electronic diary reporting irregularities (e.g. missed study medication or excessive rescue bisacodyl use, reporting compliance). Subjects will be queried for any adverse events or changes to their concomitant medications. Samples for chemistry, hematology ,urinalysis and PK will be repeated as outlined in Section 4.1. Subjects suspected by the Investigator of having developed lactic acidosis (as described in Section 4.3.3) should return for a redraw to test for lactate.

4.3.5. Day 194 Follow-up Telephone Call: +/- 3 days

At Day 194, approximately 2 weeks after the last study visit or early term visit, site personnel will contact subjects by telephone to query if any new adverse events have occurred and if any adverse events ongoing at Visit 8 have resolved. Subjects will also be asked about the status of their concomitant medications.

Confidential

Braintree Laboratories, Inc.

Protocol Number BLI400-302 Amendment#1

4.4. Tabulated Study Procedures

The following graphically depicts the flow of study procedures at each visit.

Procedures	Visit 1 Screening	Visit 2 Day 0	Visits 3 - 7 Days: 28, 56, 84, 112, 140 +/-2 days	Visit 8/ ET Day 180 +4 days	Day 194
Informed Consent	Х			,	
Inclusion/Exclusion Criteria Review	Х				
Medical History	Х				
Physical Examination	Х			Х	
Vital Signs	Х	Х	Х	Х	
Electrocardiogram	Х			Х	
Review of Concomitant Medication	Х	Х	Х	Х	Х
Dispense Electronic Diary	Х	Х	Х		
Review Diary Compliance		Х	Х		
Blood Samples for Chemistry & Hematology Testing ²	Х		X	X	
Pharmacokinetics (PK) Sample	Х		Х	Х	
Urine Sample for Urinalysis	Х		Х	Х	
Dispense Rescue Bisacodyl	Х	Х	Х		
Randomize Eligible Subjects		Х			
Dispense Study Drug ¹		Х	Х		
Study Drug and Rescue Bisacodyl Accountability		Х	Х	Х	
Assess Safety		Х	Х	Х	Х

¹Two bottles of study medication will be dispensed at Visit 7 (Day 140) ²Serum pregnancy testing will be performed at Visit 1 (Screening), Visit 5 (Day 84) and Visit 8 (Day 180) only

4.5. Pregnancy

Subjects who are female and of childbearing potential must have a serum pregnancy test done at Visit 1. A positive result will rule out the participation of the subject in the study. Additional serum pregnancy tests will be performed at Visits 5 and 8. If a subject becomes pregnant during the study, the subject must be removed from the study and followed until one month after the end of the pregnancy.

Female study subjects must be surgically sterilized or using oral contraceptives, depot contraceptives, double-barrier method, intrauterine device, or testifies that she is monogamous with a vasectomized partner. Subjects practicing abstinence must agree to use an acceptable form of birth control should they become sexually active during the study.

Women with a history of bilateral tubal ligation are not considered of childbearing potential and are not required to have a pregnancy test at screening.

Oral contraceptives, hormone implants, and injections are only considered effective if started at least 1 month before the study.

Menopausal status is defined when menses have been absent for 12 months in a woman of appropriate age (usually 45 to 55 years) who has no other suspected or identified cause of amenorrhea.

4.6. Concomitant Medications

The use of concomitant medication will be recorded from 7 days prior to Visit 1 until the end of the study at the telephone contact on Day 194. Subjects enrolled in this study will not be permitted to take any laxatives (other than the sponsor supplied rescue bisacodyl), whether prescription or over-the-counter, from Visit 1 until after completion of Treatment Day 180. Any restricted laxative use during the study may result in termination of subject's participation. Subjects may not initiate treatment with any constipating medication.

5. **ADVERSE EVENTS**

5.1. Adverse Event Definition and Reporting

An Adverse Event (AE) is any untoward medical occurrence associated with the use of a drug in humans, whether or not considered drug related. An AE can therefore be any unfavorable and unintended sign (inluding a clinically significant abnormal laboratory finding), symptom, or disease temporally associated with the use of a medicinal (investigational) product.

Adverse event collection will coincide with the subjects providing informed consent to participate in the study and will conclude with the end of study participation at Day 194 (2 week follow-up phone call). Diarrhea should be reported as an adverse event if a subject has more than 3 watery stools per day (Bristol Stool Rating = 7). Subjects with clinically significant laboratory results at Visit 8 which are classified by the Investigator as adverse events should return for a repeat blood draw. Subjects will be instructed to report promptly adverse events to the Investigator. The Investigator will record date/time of report, date/time of onset, description of the adverse event, severity of adverse event, action(s) taken regarding study participation, duration of adverse event, and the Investigator's assessment of relationship of adverse event to study treatment.

The Investigator should assess the severity of each adverse event using the following categories:

Grade	Severity	Description	
1	Mild	Barely noticeable, does not influence functioning	
	MIIId	Causing no limitations of usual activities	
2	Moderate	Makes participant uncomfortable, influences functioning	
	Moderate	Causing some limitations of usual activities	
3		Severe discomfort, treatment needed	
	Severe	Severe and undesirable, causing inability to carry out usual	
		Activities	
4	Life	Immediate risk of death	
	threatening	Life threatening or disabling	
5	Fatal	Causes death of the participant	

The Investigator should assess the relationship to study drug for each adverse event using the following categories:

Categories of Attribution:	Description
UNRELATED	There is no evidence of any causal relationship.
POSSIBLE	There is some evidence to suggest a causal relationship (e.g., the event occurred within a reasonable time after administration of the trial medication). However, the influence of other factors may have contributed to the event (e.g., the patient's clinical condition, other concomitant events).
PROBABLE	There is evidence to suggest a causal relationship, and the influence of other factors is unlikely .
DEFINITE	There is clear evidence to suggest a causal relationship, and other possible contributing factors can be ruled out .

In published Phase 3 studies, adverse events associated with BLI400 administered at doses required for effective treatment of constipation included flatulence, nausea, vomiting, abdominal cramping or pain and bloating. These adverse reactions were transient and subsided rapidly upon dose adjustment or cessation.

6. SERIOUS ADVERSE REACTIONS AND DISCONTINUATION OF STUDY

A Serious Adverse Event (SAE) is any untoward medical occurrence that results in at least one of the following outcomes:

- Results in death
- Is life-threatening
- Requires inpatient hospitalization or prolongation of existing hospitalization
- A persistent or significant incapacity or substantial disruption of the ability to conduct normal life functions
- Is a congenital anomaly/birth defect
- Requires medical or surgical intervention to prevent permanent impairment or damage

Confidential

SAE collection will coincide with the subject providing informed consent to participate in the study and will conclude 30 days after a subjects's last dose of study medication. Should a serious and/or unexpected adverse event occur, the Investigator must notify Braintree Laboratories immediately. The Investigator will make a decision regarding continuing the subject's study participation, and may request input from Braintree Laboratories. The Investigator will be responsible for recommending or providing the subject with appropriate medical therapy. All subjects experiencing serious adverse events will be followed until satisfactory resolution occurs. Braintree Laboratories must be kept apprised of all follow-ups relative to serious adverse events. In addition, Investigators must comply with the SAE reporting requirements of the Institutional Review Board with oversight of the study.

Any serious and/or unexpected adverse events that occur during the study will be reported to Braintree Laboratories as follows:

Contact Telephone Numbers:

During Business hours (M-F, 8:30 am - 5:00 pm EDT)

After hours or weekends

Braintree Laboratories and its medical monitor will review the report and determine whether an FDA Form 3500A will also be completed and sent to FDA.

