Analysis of safety will be performed using the modified Intent-to-Treat population (see Section 9.4). Safety analyses may also be presented by age, gender and racial subgroup.

Adverse Events

Adverse Events will be coded using the MedDRA classification to provide a preferred term and primary system organ class for each event. Proportions of subjects with adverse events will be presented by treatment group. Tables of AEs will be presented by system organ class and preferred term, and include overall totals for AEs within each system organ class. Counting will be done by subject and not by event. A table of counts and percentages will also be made of those subjects with SAEs or AEs which led to withdrawal from the study.

Treatment-emergent AEs are defined as adverse events that had an onset day and time on or after the day and time of the first dose of study drug up to 14 days after the last dose of

study medication. Adverse Events having missing onset dates will be considered as treatment-emergent.

The difference in adverse event rates between study groups will be tested by Chi-Square or Fisher's exact test with 95% confidence intervals. Adverse events will be presented for the overall Treatment Period.

Laboratory Parameters

Summary statistics (i.e., mean, minimum, maximum, standard deviation, and number of subjects) will be presented for each treatment group for each laboratory parameter at each visit. When calculating the summary statistics only, the last observation within a visit window will be used if there are multiple observations. Changes from Visit 1 (Screening) will be presented in a similar format. An additional listing will be provided of those subjects who have clinically significant laboratory values. The data will also be presented as shift tables, and clinically significant abnormalities will be examined.

Results of laboratory tests for the change from Visit 1 (Screening) and group differences will be tested using ANOVA.

Vital Signs

Summary statistics (i.e., mean, minimum, maximum, standard deviation, and number of subjects) will be presented for each treatment group for each vital sign at each visit. When calculating the summary statistics only, the last observation within a visit window will be used if there are multiple observations. The data will also be presented as shift tables and clinically significant abnormalities will be examined.

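### For subjects who dose to Visit 8, no scheduled contact closes the 30-day SAE window, the visit tolerances can cut the 14-day treatment-emergent window short, and the early-termination call has two anchors

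*Combined protocol and SAP*

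**What the plan says.** Four sections define how long safety data are gathered after dosing.

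- Section 6: SAE collection starts at consent and "will conclude 30 days after a subjects's last dose of study medication".
- Section 5.1: adverse event collection starts at consent and "will conclude with the end of study participation at Day 194 (2 week follow-up phone call").
- Section 9.3.3, Adverse Events: an event is treatment-emergent if its onset is "on or after the day and time of the first dose of study drug up to 14 days after the last dose of" study medication.
- Section 4.3.5: the last contact is headed "Day 194 Follow-up Telephone Call: +/- 3 days", and its text places the call "At Day 194, approximately 2 weeks after the last study visit or early term visit".

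The final clinic visit (Section 4.3.4) comes after "approximately 180 days of dosing (+4 days"), so on Day 180 to 184. Section 4 ties visit scheduling to Day 0 and says that deviations must not accumulate. The table in Section 4.4 has no column after Day 194, and Section 4.6 treats the Day 194 call as the end of the study for recording concomitant medication.

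**The concern.** The end of safety follow-up is set in three ways: 30 days after last dose for SAEs, 14 days after last dose for treatment-emergent events, and a call labelled with a calendar day for adverse event collection and participation. Only the first two move with the subject's last dose.

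Take an SAE on Day 200 in a subject whose last dose was on Day 180. It lies inside the Section 6 window. It also lies after the point at which Sections 5.1 and 4.6 have closed adverse event collection, participation and medication recording. A site cannot tell from the text how it is meant to learn of such an event.

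At stake is whether a reported 30-day SAE count means what it says, and whether treatment-emergent counts rest on the same length of questioning for each subject. Early terminators matter most here, because Section 8.2 includes subjects who stop for an adverse event or intolerance, and for them the timing of the call is ambiguous.

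**Working it through.** **Inputs.** Visit 8: Day 180 to 184 (Sections 4.3.4, 4.4). Call: Day 194 ± 3, so Day 191 to 197 (Section 4.3.5). Treatment-emergent window: last dose + 14 days (Section 9.3.3). SAE window: last dose + 30 days (Section 6). Assumption: last dose falls on the Visit 8 day, since the documents do not state the last dosing day.

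**The plan's own figure.** Nominal gap = 194 − 180 = 14 days. This reproduces the stated two weeks and equals the treatment-emergent limit.

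**Reading A: call fixed to Day 194 ± 3.** Gap = call day − last-dose day. Days without a scheduled contact = window length − gap, with a floor of 0.

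| Last dose | Call | Gap | Treatment-emergent days after call (of 14) | SAE days after call (of 30) |
|---|---|---|---|---|
| Day 180 | Day 191 | 11 | 3 | 19 |
| Day 180 | Day 194 | 14 | 0 | 16 |
| Day 180 | Day 197 | 17 | 0 | 13 |
| Day 184 | Day 191 | 7 | 7 | 23 |
| Day 184 | Day 194 | 10 | 4 | 20 |
| Day 184 | Day 197 | 13 | 1 | 17 |

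The gap runs from 191 − 184 = 7 to 197 − 180 = 17 days. The SAE shortfall is 13 to 23 days (13/30 = 43% to 23/30 = 77%). The treatment-emergent shortfall is 0 to 7 days (at most 7/14 = 50%). With last dose on Day 184 the treatment-emergent window ends on Day 198, one day after the latest permitted call. Of the 5 × 7 = 35 permitted day pairs, 3 + 4 + 5 + 6 + 7 = 25 have a gap under 14 days and none reaches 30. These are counts of permitted pairs, not probabilities.

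**Reading B: call timed from the actual visit, 14 ± 3 days.** The gap is 11 to 17 days. The SAE shortfall is 30 − 17 = 13 to 30 − 11 = 19 days. The treatment-emergent shortfall is at most 14 − 11 = 3 days, and 3 of the 7 permitted call days fall short.

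**Dosing that stops before the visit.** If last dose is k days before Visit 8, every gap grows by k: 7 + k to 17 + k under A, 11 + k to 17 + k under B. Under A, a last dose on or before Day 161 is always followed by a call at least 191 − 161 = 30 days later, so both windows are covered.

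**Early terminators.** As an illustration, let last dose and the early-termination visit both fall on Day 60. Timed from the visit, the call is at about Day 60 + 14 = 74, and 30 − 14 = 16 SAE days follow it. Fixed to Day 194, it comes 194 − 60 = 134 days after last dose. The two readings are 120 days apart: one leaves SAE days after the last contact, the other leaves a long recall period.

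**The case against.** The strongest reply is that the plan mostly works as drawn. On the nominal schedule the call falls exactly at the treatment-emergent limit, so that window is missed only through visit tolerances. The 7-day gap needs several things together: Visit 8 on its last permitted day, the call on its first, dosing through Day 184, and a call fixed to Day 194. Section 4 ties visits to Day 0 but does not mention the telephone call. All of this stands, which is why Reading B is shown beside Reading A.

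Nor is an SAE window longer than the adverse event window wrong in itself. Section 6 speaks of collection, not of questioning subjects. Section 5.1 tells subjects to report events promptly, and Section 6 requires investigators to notify the sponsor and follow SAEs to resolution. A reader might therefore go too far by inferring that SAEs after the call are not collected at all. The documents do not support that; such events can still arrive unsolicited. What subjects are told about later reporting cannot be judged, because the consent pages are not in the reviewed text. The conflict with Section 5.1, which ends participation at the call, remains.

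The effect on results is also likely to be small. At most 7 days are lost against about 194 days on study from randomization (7/194 = 3.6%). Section 5.1 describes the known reactions as transient and quick to subside once treatment is adjusted or stopped. The call schedule is the same in both arms of a double-blind trial, so no bias between arms is shown.

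**Conclusion.** The point holds, at modest weight. The SAE limb is the firm one. For subjects who dose to Visit 8, no permitted call reaches 30 days after last dose; 13 to 23 days (call fixed to Day 194) or 13 to 19 days (call timed from the visit) follow the last scheduled contact. Sections 5.1 and 6 give different ends to collection, with no procedure linking them. The treatment-emergent limb is weaker: met nominally, and cut short by at most 7 or 3 days when tolerances are used. The double anchor for early terminators in Section 4.3.5 is a plain ambiguity.

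These figures assume last dose on the Visit 8 day. A reader might infer that all of the roughly 600 randomized subjects are affected to this extent. The documents do not support that: 600 is the number to be randomized, and anyone who stops dosing before Visit 8 has a longer gap, in some cases long enough to cover both windows. A reader might also put the two windows on a level as equally unobserved; the nominal schedule contradicts this. The consequence is for completeness and consistency of safety ascertainment, not for the treatment comparison or the primary endpoint.

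**What to change.** Reconcile Sections 4.3.5, 5.1, 6 and 9.3.3 as follows.

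1. Time the existing call from the subject's last dose, by one rule for completers and early terminators, with a tolerance that does not let it fall before the treatment-emergent window ends. For example, keeping only the later side of the present tolerance gives 14 to 17 days after last dose.
2. State in Sections 5.1 and 6 whether SAE collection continues after the call. If it does, say that it is then by unsolicited report, so that the two sections agree on when collection ends.

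The cost is a wording amendment and a re-timed call, with no new visit. In the example, the earliest call for last dose on Day 180 to 184 moves from Day 191 to Day 194 to 198, so 3 to 7 days later, with slightly longer participation and recall. SAE days after the call become 30 − 17 = 13 to 30 − 14 = 16. The SAE text would then claim less than active 30-day follow-up. Moving the call out to 30 days, or shortening the SAE window to match the call, would also remove the mismatch. The first lengthens recall and the second reduces surveillance, so neither is a clear improvement; the choice is the sponsor's.
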